3.4.2. Missing PRO data

Missing data can be classified by:

- i. Extent of missingness:
 - missing items (one or more missing responses within a questionnaire); or
 - missing forms (the whole questionnaire is missing for a patient)
- ii. Reason for missingness:
 - missing completely at random (MCAR): missing data is independent of all responses (i.e. loss completely by chance); or
 - missing at random (MAR): missing data depends on other observed responses but independent of the value of the unobserved response; or
 - missing not at random (MNAR): missing data depends on the value of the unobserved response

There are two important potential consequences of missing PRO data: (1) decreased precision (wider confidence intervals) and less power to detect statistically significant differences; (2) potential for bias in the estimation of both between (e.g. treatment effect) and within group effects (e.g. change over time).(24) For example, in oncology, patients who are sicker may be less likely to complete HRQOL questionnaires which may potentially overestimate HRQOL and underestimate the adverse effects of cancer and cancer therapy.

3.4.2.1. Missing HRQOL data patterns

Prior to conducting analyses of HRQOL data, rates and reasons for missing PRO questionnaires will be summarised to assess the extent to which data are missing at random. This is an important first step, as it aids interpretation of the results of HRQOL outcome analyses relative to the assumptions of those analyses.

A table of HRQOL completion rates by arm will be reported. Following NCIC Clinical Trials Group (NCIC CTG) recommendations(25), completion rates at each follow-up timepoint will be calculated in two ways, that is, HRQOL assessments completed as a percentage of: 1) all participants recruited (i.e. number of baseline HRQOL completions); 2) number of HRQOL assessment expected (i.e. number of participants still alive and on-study at that timepoint).

Table 2. Rate and reasons for missing ELFI data

Status/Reason	All Study Participants (N=)			
	Week 0	Week 12	Week 18	Week 24
	N (%)	N (%)	N (%)	N (%)
Completed				
Patient refused				
Patient feels too ill				
Staff felt patient too ill				
Staff oversight				
Other, not specified				

Unknown				
Patient death				
% of surviving patients				
% of total patients				

Table 3. Rate and reasons for missing ELFI data, according to treatment groups

Status/Reason	Intervention Group (N=)				Usual Care Group (N=X)			
	Week 0 N (%)	Week 12 N (%)	Week 18 N (%)	Week 24 N (%)	Week 0 N (%)	Week 12 N (%)	Week 18 N (%)	Week 24 N (%)
Completed								
Patient refused								
Patient feels too ill								
Staff felt patient too ill								
Staff oversight								
Other, not specified								
Unknown								
Patient died								
% of surviving patients								
% of total patients								

To explore mechanisms of missingness, a graph of the ELFI versus time will be graphed, stratified by dropout time.(24) If the trajectories over time are substantially different, this will suggest data are not missing completely at random. For example, if participants who have lower baseline values are more likely to drop out, or if steeper rates of decrease in ELFI over time are associated with earlier dropout, missing data are more likely to be linked with sicker participants. We will also use these graphs to assess whether the separation between the missingness patterns is more dramatic in the intervention arm than the control arm.

3.4.2.2. Handling of missing PRO data: primary efficacy analysis

When at least half of the items from the relevant EORTC QLQ scale have been answered, scores for missing items will be assigned the mean score of the completed items from the relevant scale. If more than half the items are missing, then the scale score is missing.

3.4.2.3. Handling of missing PRO data: secondary efficacy analyses

The following imputation method will be applied prior to performing the relevant statistical test:

PRO	Imputation for Missing Item(s)	Imputation for Missing Form(s)
ECOG-PS	If KPS has been answered, scores for missing ECOG-PS will be imputed by multiple imputation using predictive mean matching	None
KPS	If ECOG-PS has been answered, scores for missing KPS-PS will be imputed by multiple imputation using predictive mean matching	None
ADL	If at least half of the items from the scale have been answered, scores for missing items will be assigned the mean score of the completed items	None
IADL	If at least half of the items from the scale have been answered, scores for missing items will be assigned the mean score of the completed items	None
PHQ9	If one or two values are missing from the score, then they can be substituted by the average score of the non-missing items. (instrument instructions)	None
GAD7	If one or two values are missing from the score, then they can be substituted by the average score of the non-missing items. (instrument instructions)	None
Self-MNA	If at least half of the items from the scale have been answered, scores for missing items will be imputed by multiple imputation using predictive mean matching	None
G8 score	If at least half of the items from the scale have been answered, scores for missing items will be imputed by multiple imputation using predictive mean matching	None
EQ-5D-5L	If at least 60% of the domains have been answered, scores for missing domains will be imputed by multiple imputation using predictive mean matching	None

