3.6.5.4. Study Week 12, Week 18 and Week 24 (follow-up assessments)

Follow-up assessments are evaluated at 12 weeks, 18 weeks and 24 weeks after randomisation. Assessments are permitted within the 3 weeks period prior or 3 weeks period following the assessment time-point, with preference for assessment to be done immediately before a specified treatment cycle where possible. To avoid more frequent clinic visits, the researcher will make an effort to meet with participants at their regularly scheduled visits, such as appointments with their oncologists and chemotherapy or radiotherapy sessions. At the scheduled assessment timepoints, all participants will be asked to complete a series of PRO measures (see **3.6.1.**). The times required to complete the PRO measures at week 12 is approximately 13 minutes; week 18 is approximately 3 minutes; and week 24 is approximately 13 minutes.

The researcher will also collect additional data regarding participant characteristics, disease characteristics, comorbidities, medications, chemotherapy delivery, healthcare utilisation, level of care and survival (see **Section 3.6.1.**).

For participants assigned to the intervention arm, the results of the follow-up assessments (except for the HRQoL questionnaires) will be made available to the treating clinicians. For participants assigned to the control arm, treating clinicians will be blinded to the results of the follow-up assessments.

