2.7.2.3. Activities of Daily Living (ADL) and Instrumental Activities of Daily Living (IADL)

In geriatric medicine, ADL and IADL is used to assess functional status and is part of routine geriatric assessment.(8) Decline in functional status is associated with adverse health outcomes such as mortality and residential care placement for older hospitalised patients. Self-reported Katz ADL scale and OARS IADL scale will be used to describe the functioning level in of the study population.(9, 10)

Katz ADL scale assesses adequacy of performance in basic activities of daily living: bathing, dressing, toileting, transferring, continence, and feeding. Each item are scored yes/no for independence in each of the six functions. A summary score ranges from 0 (unable to perform any activity) to 6 (able to perform all activities).

OARS IADL is an easy to administer assessment instrument that provides self-reported information about functional skills necessary for independent living in the community. These skills are considered more complex than the basic activities of daily living as measured by the Katz ADL scale. The 7-items on the OARS IADL assesses the following domains of function: telephone, shopping, food preparation, housekeeping, mode of transportation, medications and finances. Each item is scored on a 3-point Likert-like scale, with the total score ranging from 0 (unable to perform any activity) to 14 (able to perform all activities).

Disability in ADL and IADL is defined as the need for assistance to complete at least one ADL or IADL, respectively. Functional decline in ADL and IADL is defined as any decrease in ADL and/or IADL score between baseline and follow-up assessments.

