3.5.2. Other Secondary Endpoints

Other secondary endpoints will be summarised according to established guidelines specific to the measurement instrument. In general, categorical variables will be tabulated and key summary statistics (mean, standard deviation, median, range, etc.) will be presented for continuous measurements. Comparisons between treatment arms will be made where appropriate and the test selected depending on the distribution.

Secondary endpoints were specified in the protocol as follows:

- Performance Status The mean self-rated ECOG score and KPS score of patients at 12 weeks and 24 weeks are secondary endpoints; they will be compared between treatment arms.
- Functional Status The proportion of participants in each treatment arm with functional decline in the ADL and/or IADL scores at 12 weeks and 24 weeks are secondary endpoints of this study; they will be compared between treatment arms.
- Mood The proportion of participants in each of the PHQ-9 and GAD-7 categories (cut-points 5, 10 and 15) in the two treatment arms at 12 weeks and 24 weeks are secondary endpoints of this study; they will be compared between treatment arms.
- Nutrition The proportion of participants with self-MNA score ≤ 11 points and >11 points in the two treatment arms at 12 weeks and 24 weeks is a secondary endpoint of this study and will be compared between treatment arms.
- Health Utility The EQ-5D-5L health utility score in the two treatment arms at 12 weeks and 24 weeks are secondary endpoints of this study and will be compared between treatment arms.
- Chemotherapy delivery Secondary endpoints of this study are the mean RDI of chemotherapy, the proportion of participants with dose reduction $\geq 10\%$ from previous dose; they will be compared between treatment arms.
- Healthcare utilisation Secondary endpoints of this study are the mean number of: emergency department visits, hospital admissions (including length of hospital stay; and divided into planned and unplanned), medical consultations and type of PBS-listed medications in the two treatment arms from randomisation to 12 weeks and 24 weeks post-randomisation; they will be compared between treatment arms. An additional secondary endpoint is the hazard ratio for hospitalisation of participants in the two treatment arms; this will be compared between treatment arms.

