- Institutionalisation A secondary endpoint of this study is the hazard ratio of institutionalisation of participants in the two treatment arms; this will be compared between treatment arms. In addition, the level of care level of care and social situation will also be described in the treatment arms.

The following endpoint definition was changed from the protocol:

- Chemotherapy delivery: the proportion of participants with dose delays in the two treatment arms at 12 weeks and 24 weeks. Dose delay is defined as a delay of more than 3 days in the start of chemotherapy measured since the start of the previous cycle.

The following endpoints were not defined in the protocol, but will be analysed as exploratory endpoints to supplement the pre-specified secondary endpoints:

- QLU-C10D health utility
- QLU-C10D health utility score in the two treatment arms at 12 weeks and 24 weeks will be compared between treatment arms.(27, 28)
- The QLU-C10D health utility scores will also be used in the health economic analysis, in place of the EQ-5D-5L scores, to determine if the same or different conclusions would be reached with either utility measure.
- Chemotherapy delivery
- Primary dose reduction (PDR) will be compared within treatment arms. PDR is defined as dose of chemotherapy which is less than the dose recommended for given regimen in current treatment guidelines by NCCN (excluding round-off).
- Mean % dose reduction at outset will be compared within treatment arms.
- Median % dose reduction at outset will be compared within treatment arms.
- Early discontinuation of chemotherapy will be compared within treatment arms.
- Mean cycles of chemotherapy delivered will be compared within treatment arms.
- Median cycles of chemotherapy delivered will be compared within treatment arms.

Table 4. Summary of secondary and additional exploratory endpoints, data type, data timepoints and statistical tests are listed in the table below.

Endpoints	Data Type	Data output	Data Timepoints	Statistical Tests
Function				
ECOG-PS	Categorical ordinal (0,1,2,3,4)	contingency table	Baseline Wk12 Wk24	contingency table analysis
KPS	Categorical ordinal (30,40,50,60,70,80,90,100)	contingency table	Baseline Wk12 Wk24	contingency table analysis
Katz ADL scale	6-item, categorical dichotomous scale (i) → dichotomous outcome (unimpaired, impaired) (ii) → dichotomous outcome (any decrease in ADL)	1. unimpaired vs impaired 2. decrease in ADL	Baseline Wk12 Wk24	contingency table analysis

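### Filling blank ADL and IADL items with the form's mean, then counting any decrease as decline, misclassifies a secondary endpoint

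*Combined protocol and SAP*

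**What the plan says.** SAP 3.4.2.3 sets the same rule for both scales: "If at least half of the items from the scale have been answered", then "scores for missing items will be assigned the mean score of the completed items". This is done before the statistical test.

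SAP 2.7.2.3 gives the scoring and the event:

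- Katz ADL: "Each item are scored yes/no for independence in each of the six functions", for a total of 0 to 6.
- OARS IADL has seven items: "Each item is scored on a 3-point Likert-like scale, with the total score ranging from 0" to 14.
- Event: "Functional decline in ADL and IADL is defined as any decrease in ADL and/or IADL score between baseline and follow-up assessments".

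SAP 3.5.2 makes this a between-arm comparison: the proportions with "functional decline in the ADL and/or IADL scores at 12 weeks and 24 weeks are secondary endpoints". Table 4 in that section repeats the any-decrease dichotomy for each scale and assigns contingency table analysis.

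The SAP gives no rounding rule, no minimum decrease, no item-by-item comparison, and no sensitivity analysis for blank ADL or IADL items. In the same table of SAP 3.4.2.3, Self-MNA and G8 items are filled by multiple imputation with predictive mean matching.

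**The concern.** Filling a blank with the patient's own mean can be reasonable when the total is used as a roughly continuous score. Here the total feeds a rule with no tolerance, so a fraction of a point below baseline is an event. The filled total matches the true one only if the blank item happens to equal the mean of the others. For a patient with mixed item scores it usually does not, so a blank answer alone can produce an apparent decline. The same rule gives a patient who answers the remaining items at full score a full total, which can conceal the one activity just lost.

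At stake is a named secondary endpoint on function. Misclassification in both directions blurs a difference between arms, and no planned sensitivity analysis would reveal it.

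**Working it through.** **Inputs.** From SAP 2.7.2.3: six yes/no ADL items, seven IADL items scored 0-2, decline = any decrease. From SAP 3.4.2.3: up to 3 of 6 or 3 of 7 items may be blank and still be filled. (The timing table in protocol 3.6.4 counts the two instruments together as 2 items; I used six and seven.) The documents give no figure for this endpoint. Their one sample size, 64 per group for the primary endpoint, reproduces: a two-sided 5% t-test at effect size 0.5 has 80.1% power. I use 64 only as the arm size.

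**Filled total** = (mean of answered items) × (number of items).

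**False decline.** No true change, complete baseline, one follow-up item blank, each position equally likely:

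| True score, both visits | Better-scored item blank | Counted as decline |
|---|---|---|
| ADL 5 | 4/5 × 6 = 4.8 | 5 of 6 positions |
| ADL 4 | 3/5 × 6 = 3.6 | 4 of 6 |
| ADL 3 | 2/5 × 6 = 2.4 | 3 of 6 |
| IADL 13 (one item at 1) | 11/6 × 7 = 12.83 | 6 of 7 |
| IADL 12 (one item at 0) | 10/6 × 7 = 11.67 | 6 of 7 |
| ADL 6 or IADL 14 | stays 6 or 14 | never |

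A baseline blank can do the same. A true ADL of 5 with the dependent item blank scores 5/5 × 6 = 6, so a complete follow-up of 5 is a decline (1 of 6 positions).

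**Hidden decline.** ADL 6 to 5 with the lost item blank scores 5/5 × 6 = 6. This happens in 1/6, 1/3 and 1/2 of placements with one, two and three blanks. For IADL 14 to 13 the shares are 1/7, 2/7 and 3/7.

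**Size, under assumptions.** Let 10-20% have an ADL impairment and 30-50% an IADL impairment, with items blank at random at rate p at both visits. To first order, with one impaired item, false decline among unchanged patients is (IADL share × 7p) + (ADL share × 6p). At p = 1%:

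- lower: 0.30 × 7% + 0.10 × 6% = 2.7%
- upper: 0.50 × 7% + 0.20 × 6% = 4.7%

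Simulation of 100,000 patients per scenario, with assumed true decline of 50% (control) and 25% (intervention), gives for the control arm:

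| p per item | Forms with a blank, 1-(1-p)^6 / 1-(1-p)^7 | False decline, unchanged patients | Hidden, true decliners |
|---|---|---|---|
| 0.5% | 3.0% / 3.4% | 1.4-2.4% | 0.5% |
| 1% | 5.9% / 6.8% | 2.5-4.3% | 1% |
| 3% | 16.7% / 19.2% | 6.2-10.9% | 3% |

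If impaired items are three times as likely to be blank, hidden decline is about 3% at p = 1% and 9% at 3%.

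**Effect on the contrast.** At p = 3% the true difference of about 25 points is counted as 51.4 - 28.8 = 22.6 points (lower impairment) or 54.1 - 32.3 = 21.8 points (upper). Power with 64 per arm falls from 84% to 81-83% at p = 1% and to 71-75% at p = 3%.

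**Comparing only items answered at both visits.** A patient whose item scores are unchanged can no longer be a false decline. For a decline on one item, hidden decline becomes about 1-(1-p)^2, that is 2.0% at p = 1% and 5.9% at 3%. Total control-arm misclassification at p = 3% moves from 0.5 × 6.2% + 0.5 × 3.1% = 4.7% (lower), or 0.5 × 10.9% + 0.5 × 3.2% = 7.1% (upper), to about 0.5 × 5.9% = 3.0%. Power is about 81%.

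**The case against.** **Rounding.** Item scores are whole numbers, and a programmer might round imputed items: 0.8 becomes 1 and 1.67 becomes 2, so the ADL 5 and IADL 12 examples vanish. That is correct, but the SAP does not say so. Rounding is also incomplete: at ADL 3 the imputed 2/5 = 0.4 rounds to 0, giving 2 < 3, and hidden decline is untouched.

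**Blanks may be rare.** Protocol 3.6.6 has the researcher contact participants when part of an assessment is missed, with up to three reminder calls for posted questionnaires. This stands as a limit on size. At 1% blanks per item, false declines number about one or two patients per arm of 64 (2.5% of 32 unchanged controls = 0.8; 4.1% of 48 unchanged intervention patients = 2.0). The larger figures need blank rates that the documents neither state nor exclude. Forms are on paper and completed without staff help (protocol 3.6.3), and the imputation rule itself anticipates blanks.

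**A stronger reading: bias towards the intervention.** Protocol 3.6.5.4 lets the patients' own doctors see these forms in one arm only: "For participants assigned to the intervention arm, the results of the follow-up assessments (except for the HRQoL questionnaires) will be made available to the treating". A reader might infer that blanks are noticed and completed more often in that arm, leaving extra false declines in controls. The documents do not support this. They do not ask clinicians to check forms for gaps, and the chasing of missing parts in protocol 3.6.6 makes no distinction by arm. Even if blanks were commoner in controls, both false and hidden decline would rise there, so the net direction would be open.

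**Changing the endpoint.** Redefining decline as a worse score on any single item would reclassify patients with complete forms whose gains and losses cancel. That objection is sound, and the fix below avoids it by still comparing totals.

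**Conclusion.** The misclassification follows directly from the SAP's scoring, imputation and decline rules, read without rounding. False decline is confined to patients whose item scores are not all equal; an unchanged patient at full score is never affected. With a single follow-up blank, hidden decline was found for patients starting at full score.

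The size is not known from the documents. Under the assumed impairment rates and random blanks, roughly 1-4% of unchanged patients are false declines at 0.5-1% blanks per item, and 6-11% at 3%. The power figures also rest on an assumed 50% versus 25% decline; the trial was not sized for this endpoint. With equal blank rates in the two arms the main consequence is dilution of the contrast, and no direction of arm bias is shown. ELFI has its own missing-item rule (SAP 3.4.2.2), so the primary endpoint and the 64 per group are unaffected.

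This should be corrected because a stated rule gives wrong classifications and the remedy is cheap. It does not threaten the trial's main conclusion.

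**What to change.** In SAP 3.4.2.3, for the decline endpoint only, replace mean imputation with: *compare the baseline and follow-up totals over the items answered at both visits; decline is a lower total on those common items; the result is missing if fewer than half of the items are answered at both visits.* Cross-refer to this from SAP 2.7.2.3 and Table 4 in 3.5.2. Keep mean imputation for descriptive totals. Patients with complete forms are classified exactly as now.

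Add one sensitivity analysis: item-level multiple imputation with predictive mean matching, the method already used in that table for Self-MNA and G8. Its performance here was not simulated.

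Costs: a short SAP amendment and simple programming, with no new data. Hidden decline rises from about 1% to 2% of true decliners at 1% blanks per item, and from 3% to 6% at 3%. A few patients with different items blank at the two visits become missing. A patient whose item changes cancel out can still be misclassified if one of those items is blank.

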3.4.3. Primary HRQOL Analysis

The primary HRQOL analysis is defined prospectively as a comparison of the longitudinal change in ELFI scores for significant between-group difference using linear mixed models. The models will include baseline variables (baseline ELFI score, and possibly other baseline variables predictive of ELFI outcome) as covariates and treatment arm and time (and their interaction) as fixed effects. Time will include the baseline, 12 week, 18 week and 24 week assessment points. Time is continuous in linear mixed model.

These models account for covariance between repeated measures on participants and will be used to: i) describe the time course of the ELFI over time; ii) assess whether the time course differs between the two treatment arms by testing the study arm-by-time interaction; and iii) estimate and test differences between the two treatment arms at specific time points of interest via selected linear contrasts.

Linear mixed models account for missing data by using information from the observed data to implicitly impute unobserved data.

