4.3.3. Primary HRQoL Analysis

The primary HRQoL analysis is defined prospectively as a comparison of the longitudinal change in TOI scores for significant between-group difference using linear mixed models. The models will include baseline variables (baseline TOI score, and possibly other baseline variables predictive of TOI outcome) as covariates and treatment arm and time (and their interaction) as fixed effects. Time will include the baseline, 12 week, 18 week and 24 week time-points.

These models account for covariance between repeated measures on participants and will be used to: i) describe the time course of the TOI over time; ii) assess whether the time course differs between the two treatment arms by testing the study arm-by-time interaction; and iii) estimate and test differences between the two treatment arms at specific time points of interest via selected linear contrasts. Sensitivity analyses will be performed using pattern-mixture models and/or joint model of longitudinal and survival data to help interpret results if greater than 20% of the TOI data are missing, and if reasons for missing data (from the CoMiDa form) and patterns of missing data (described in **Section 4.3.2.**) suggest that these when data are not missing at random.

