2.3. Treatment Allocation

2.3.1. Method of Treatment Allocation

Participants were randomly assigned via a computerised system using the method of minimisation (with a 80:20 random element) to receive integrated geriatric care or standard oncology care in a 1:1 ratio.(1) In this study, minimisation was used to achieve balance between groups using the following characteristics:

- treatment intent
- tumour type
- age
- gender
- ECOG performance status (physician-rated)

An 80:20 random element was determined to be the optimal value to reduce predictability whilst retaining balance.(2) This method was conducted using the MinimPy software package by a researcher not involved in the care of the study participants.(3)

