3.2. Sample size

3.2.1. Sample size required

Based on reviews of published studies, a minimal important difference in patient-reported outcome scores has commonly been set at approximately half the standard deviation; that is, equivalent to an effect size of 0.50.(20, 21) An effect size of 0.5 is commonly regarded as a medium difference and a meta-analysis has shown it to be clinically relevant in studies of quality of life using QLQ-C30 as an outcome measure.(22, 23)

The target sample for this study was based on an independent t-test at a 2-sided significance level of 0.05 to have an 80% power to detect a significant between-group difference in ELFI from baseline to 12 weeks with an effect size of 0.5. Under these assumptions, the minimum sample size is 64 evaluable participants in each group (or a total of approximately 128 evaluable participants) who have completed the primary outcome measure at two separate timepoints.

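### The primary mixed model uses baseline ELFI as both response and covariate and names only one continuous time term, so its week-12 contrast is right only if the arm difference grows in a straight line from zero

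*Combined protocol and SAP*

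**What the plan says.** SAP 3.4.3 defines the primary analysis as a linear mixed model for longitudinal change in ELFI. On baseline it says: "The models will include baseline variables (baseline ELFI score, and possibly other baseline variables predictive of ELFI outcome) as covariates". Arm, time and their interaction are the fixed effects. On time it says: "Time will include the baseline, 12 week, 18 week and 24 week assessment points. Time is continuous in linear mixed model". The model serves to test the arm-by-time interaction and also to "estimate and test differences between the two treatment arms at specific time points of interest via selected linear contrasts". SAP 3.4.6 applies Hochberg's method to those time-specific comparisons.

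Protocol 4.3.3 has the same double use of baseline ("Time will include the baseline, 12 week, 18 week and 24 week time-points") but does not say whether time is continuous or categorical. The SAP added that.

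The sample size in SAP 3.2.1 rests on an "independent t-test at a 2-sided significance level of 0.05 to have an 80% power" for a "between-group difference in ELFI from baseline to 12 weeks with an effect size of 0.5". SAP 3.4.5 also plans a t-test or Wilcoxon test of ELFI change at 12, 18 and 24 weeks, but only as a tertiary analysis.

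**The concern.** There are two separate problems.

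- **Baseline is used twice.** At week 0 the response equals the covariate. One covariate coefficient then has to serve a visit where the relation is exactly 1 and later visits where it is weaker. An unstructured covariance cannot be combined with this, because the week-0 residual variance given the covariate is zero.
- **Time is a single continuous term.** Read as a straight line, the arm differences at weeks 12, 18 and 24 all come from two arm parameters, an intercept and a slope. They are not estimates of what happened at each visit.

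Week 12 is the time point that the trial was sized on. If the arm difference is not linear from zero, the primary model can report the wrong week-12 difference, or miss an early effect in the interaction test, while appearing to be a baseline-adjusted analysis.

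**Working it through.** **Inputs.** From SAP 3.2.1: effect 0.5 SD, two-sided 0.05, 80% power, 64 per arm. From SAP 2.3.1: 1:1 allocation. From SAP 3.4.3: visits at 0, 12, 18 and 24 weeks. Assumed, because the documents give no figure: the shape of the true effect, a random intercept (equal correlation between visits), and a correlation of 0.5 or 0.7. Effects are in SDs of the baseline-to-follow-up change.

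**Step 1: the plan's own figure.** The exact two-sample t-test needs 63.77 per arm, rounded up to 64, with 80.1% power. The stated sample size reproduces.

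**Step 2: what the straight line reports at week 12.** The mean visit time is (0+12+18+24)/4 = 13.5. Sxx = 13.5² + 1.5² + 4.5² + 10.5² = 315. The fitted difference at week 12 gives visit t the weight 1/4 + (12 − 13.5)(t − 13.5)/315:

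- week 0: 0.25 + 0.0643 = 0.314
- week 12: 0.25 + 0.0071 = 0.257
- week 18: 0.25 − 0.0214 = 0.229
- week 24: 0.25 − 0.0500 = 0.200

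The same formula for week 24 gives −0.2, 0.2, 0.4, 0.6. The slope weights are (t − 13.5)/315. Randomisation makes the expected baseline difference zero, so the covariate does not change these averages.

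| True difference at weeks 12, 18, 24 | Fitted, week 12 | Fitted, week 24 | Slope per week |
|---|---|---|---|
| 0.50, 0.75, 1.00 (linear) | 0.50 | 1.00 | 0.0417 |
| 0.50, 0.50, 0.50 (plateau) | 0.34 | 0.60 | 0.0214 |
| 0.50, 0.25, 0 (fading) | 0.19 | 0.20 | 0.0012 |
| 0, 0.25, 0.50 (late) | 0.16 | 0.40 | 0.0202 |

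For example, the plateau is 0.50 × (0.257 + 0.229 + 0.200) = 0.34.

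**Step 3: power of the interaction test.** With complete data and a random intercept, the SE of the slope difference, in SDs of change, is 1/√(64 × 315) = 0.00704 per week, whatever the correlation.

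- Plateau: 0.0214/0.00704 = 3.04; power Φ(3.04 − 1.96) = 86%. Simulation: 86%.
- Fading: 0.0012/0.00704 = 0.17; two-sided power about 5%. Simulation: 4.9%.

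Simulations used 6,000 trials per setting. The model's own week-12 contrast rejected in 98% (correlation 0.5) and 96% (0.7) under the plateau, and in 57% and 48% under fading. With post-baseline responses, categorical time and baseline as covariate, the week-12 contrast recovered the true difference under every shape tried, with power of about 90% and 86–87%.

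**Step 4: what the covariate does.** In complete balanced data the arm-by-time estimate is the difference in mean within-person slopes. A covariate that is constant within a person cancels. Two fits with and without it agreed to five decimals (slope × 12: 0.19866, SE 0.08024; and 0.11922, SE 0.07820). The 24-week slope difference moves with a chance baseline imbalance by −24 × 0.04286 × (1 − correlation): −0.51 at 0.5 and −0.31 at 0.7, as an unadjusted change score does. With about 17%, 28% and 37% missing at random at the three follow-up visits, adding the covariate changed the estimate by 0.015 on average, against an SD of 0.094.

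**Step 5: double use alone.** With categorical time and baseline still in both places, the mean week-12 estimate was 0.50 for a true 0.50. It moved by about −0.13 per unit of baseline imbalance at correlation 0.5.

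**Step 6: no effect.** The interaction test rejected in 5.0–5.3% and the week-12 contrast in 3.3%.

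**The case against.** The strongest defence is that SAP 1.3 hypothesises a benefit on the rate of decline as well as its size, so a slope test is legitimate, and week 12 is the sizing time point but not the declared sole estimand. The documents do not settle the effect shape. The geriatric assessment comes within 3 weeks of randomisation, which allows an early effect. Reviews at 12 and 24 weeks and a mixed population of treatments and intents allow a growing one. For a difference growing 0.25, 0.375, 0.50, the interaction test has 84% power against 33–36% for a baseline-adjusted week-12 contrast. Continuous time does not strictly exclude a curve, and it handles assessments away from the nominal week. SAP 3.4.5 tests the week-12 change directly.

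Most of this stands and limits the point. It does not remove it. No curve is specified, the tertiary test does not repair the primary model, and baseline still has two roles in one equation.

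A reader might infer three stronger things that are not supported:

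- **That the week-12 estimate is biased as such.** The bias needs an arm difference that is not linear from zero. Curvature shared by both arms does no harm, and double use of baseline alone causes no average bias.
- **That baseline is ignored in the interaction test.** It is differenced, because week 0 is a response. What is missing is adjustment of the ANCOVA kind, and that is exact only for complete data with a random intercept.
- **That false positives are inflated.** Among simulated null trials with a baseline imbalance above 0.2 SD, rejection was 9–10%, but it was 3–4% in the rest and close to 5% overall, as for any change-score test.

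**Conclusion.** The concern holds as a defect of specification with conditional consequences. SAP 3.4.3 does not describe one coherent model, and its baseline covariate does little or nothing for the interaction test. Under a straight line, only about a quarter of the weight in the week-12 contrast falls on week 12. A difference held from week 12 is then understated by 31% (0.34 for 0.50) and a fading one by 63% (0.19 for 0.50). A difference growing linearly from zero is estimated correctly. The loss of power in the interaction test is severe only for the fading shape. The week-12 percentages follow from the visit spacing and the assumed shape. The power figures also assume complete data and equal correlation between visits. The sample-size calculation itself is not in error.

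**What to change.** Rewrite SAP 3.4.3 so that baseline ELFI is used once. Choose one of:

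- **(a)** ELFI at weeks 0, 12, 18 and 24 as the response; time as a four-level factor; arm means constrained equal at baseline; arm-by-time terms at weeks 12, 18 and 24; unstructured within-participant covariance; no baseline covariate.
- **(b)** ELFI at weeks 12, 18 and 24 as the response; time as a factor; baseline ELFI and baseline-by-time as covariates; the covariance structure named.

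Delete the sentence that makes time continuous. Assign assessments to visits by the existing ±3-week windows (Protocol 3.6.2). Adjacent windows meet at weeks 15 and 21, so add a tie rule. Also say how a questionnaire completed at early discontinuation (Protocol 3.6.5.5) is placed. Keep the linear-slope arm-by-time test as a supportive analysis of the rate-of-decline hypothesis.

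**Cost.** This changes SAP wording only; no new data are needed. The arm-by-time test uses three degrees of freedom where it used one. An unstructured covariance has 4 × 5/2 = 10 parameters under (a) or 3 × 4/2 = 6 under (b), against two for a random intercept. If the effect grows steadily, the visit-specific contrast has less power than the slope test, which is why the slope test should stay as a supportive analysis.
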